**Schema:**

Consecutive patients presenting to Grady Memorial Hospital with mandibular fractures will be evaluated for recruitment in this pilot study. Patients requiring either open reduction and internal fixation (ORIF) or closed reduction (CR) will be included in the study.

The choice of surgical method (ORIF versus CR) will be determined by the patient preference in conjunction with the attending surgeons expert opinion. The surgical procedure for closed treatment is a simple and standardized procedure involving placement of arch bars and maxillomandibular fixation (MMF) for a period of 4-6 weeks. The surgical procedure for ORIF will involve the placement of arch bars intraoperatively, exposure of fractures by intraoral or transcutaneous incisions, intraoperative MMF and ORIF. All procedures will be done under a general anesthesia. All eligible subjects will be initially stratified to ORIF or CR. Subjects within each group will then be randomized to either Stryker Hybrid arch bars or Erich arch bars (control). In all groups the arch bars will be left in place for six weeks. Stryker Hybrid arch bars will be placed according to the manufacturers instruction using a minimum of four locking screws per arch. Erich arch bars will be placed using a combination of 24 and 25 gauge wire as is the historical technique. Arch bar removal is a simple procedure that will be completed under local anesthesia in the outpatient clinic.

The primary predictor variable is the type of archbar (Stryker Hybrid versus Erich). The primary outcome variable is time required to place the arch bars. Secondary outcomes include union (nonunion, fibrous union, malunion), complications, hospital charges and need for additional procedures

**Introduction:**

Mandible fractures are commonly a result of maxillofacial trauma and account for the majority of facial fractures. The majority of fractures are treated with either ORIF or CR. Erich arch bars are the most commonly used type of MMF and are considered the gold standard. However, the application of Erich arch bars is time-consuming and requires the presence of teeth. Intermaxillary fixation screws and IVY loops are alternative approaches that may also be used. The hybrid arch bar system developed by Stryker is unique in that the bars are secured to the underlying alveolar bone with self-drilling locking screws rather than the teeth. This potentially reduces the time required to place the arch bars as well as the need for teeth.

There are no studies comparing Stryker Hybrid arch bars to traditional methods of MMF.

## Objectives

- 1) Is there a difference in the application time when comparing Stryker hybrid arch bars to Erich arch bars for the ORIF or CR of mandibular fractures?
- 2) Is there any difference in overall surgical time, postoperative length of stay, hospital charges, fracture healing or complications when comparing Stryker hybrid arch bars to Erich arch bars for the ORIF or CR of mandibular fractures?

## Patient Selection

Patients presenting to Grady Memorial Hospital will be eligible for inclusion in the study.

### Inclusion Criteria:

- 1) Mandible fracture involving subcondyle, ramus, angle, body, parasymphysis and symphysis
- 2) Age 18 years - 90 years
- 3) Ability to give informed consent
- 4) Minimum 6 weeks follow-up
- 5) Pre and post-operative panoramic xrays

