## Pretreatment Evaluation

All patients will have a history and physical examination as part of their admission to Grady Memorial Hospital. All patients will have a panorex xray or maxillofacial CT scan to assess the severity and location of mandible fractures and other facial fractures, as is the standard of care. In addition to routine blood tests (complete blood count and metabolic panel), patients reporting diabetes in their history will have a hemoglobin A1c drawn. Patients reporting human immunodeficiency virus infection in their history will have a CD4 count drawn unless they have recent result (CD4 count within 6 months) or

refuse. This will allow the level of immunocompetence in patients with known diabetes or HIV to be evaluated and additional medical care (additional antibiotics, antifungals, opportunistic infection prophylaxis, strict blood glucose control etc.) to be provided as the standard of care.

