### Registration and Randomization

Eligible patients will be offered the opportunity to enroll in the study when they are first consulted by the oral and maxillofacial surgery service. Consent will be obtained by one of the study investigators. Subjects will then be randomized to either Stryker hybrid arch bars or Erich archbars group using sealed envelopes that have been prepared by the study statistician.

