### Sample size

No prior studies exist to guide sample size calculations. It is anticipated that this pilot study will include a total of 40 subjects in the CR arms and 60 subjects in the ORIF arms. This study will allow for a drop out rate 30% for the outcome variables which is consistent with the patient population based on prior studies.

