### Therapy

In the ORIF group, thirty patients will be randomized to each arm of the study (30 Stryker hybrid arch bars and 30 Erich arch bars). In the CR group, twenty subjects will be randomized to each arm of the study (20 Stryker hybrid arch bars and 20 Erich arch bars). A number of different resident surgeons will perform the surgical treatment including the application of MMF. All residents will complete Stryker clinical skills training and will be standardized as the application process and technique for both arch bar systems. For all study subjects, time will be recorded from start to completion of maxillary and mandibular arch bar placement, and from insertion of throat pack to removal of throat pack. This will be measured using two different electronic timers to record the respective times. All arch bars will be left in place (ORIF and CR) for a period of 6 weeks. Patients will be discharged from the hospital as soon as possible after medically stable from surgery. Patients will be seen for follow up routinely for a minimum of 6 weeks postoperatively to ensure appropriate healing.

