### Patient Assessment

Patients will be assessed during surgery and in the postoperative period while in the hospital. After discharge, patients will be followed routinely to ensure complete bony consolidation of the fracture and at 4 to 12 weeks postoperatively. The primary

outcome variable is application time for placement of arch bars. Secondary outcomes include intra-operative surgical time length of stay after surgical procedure, length of stay, hospital charges, fracture healing and complications.

All data will be collected by the PI or CI during the initial admission for surgery to repair the fracture or at the one week and 6 week follow-up appointments. All data will be recorded on a standard data collection sheet. Subjects will have not have any questionnaires or surveys to complete. Demographic, preoperative, operative and postoperative variables will be recorded and analyzed. Demographic data includes age, sex and race. Preoperative variables include medical history (DM and HIV), social history, fracture location, number of fractures, time from injury to surgery and antibiotic use. Operative variables include time for arch bar application, surgical time and surgical approach. Post operative variables include fracture healing, follow-up, complications and hospital charges. It is anticipated that the study will conclude at 24 months. All subjects will be paid \$50 at the 4 to 12 week follow-up visit.

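### Inclusion criterion 4 and the post-operative half of criterion 5 describe events after randomisation; the SAP claims intent-to-treat but does not define its analysis set as all randomised patients

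*Protocol*

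**What the plan says.** The protocol's Inclusion Criteria contain five items. The fourth is "Minimum 6 weeks follow-up" and the fifth is "Pre and post-operative panoramic xrays".

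Under Registration and Randomization, "Eligible patients will be offered the opportunity to enroll in the study when they are first consulted" by the surgical service. Consent follows, and then randomisation by sealed envelope.

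Under Therapy, "For all study subjects, time will be recorded from start to completion of maxillary and mandibular arch bar placement". Surgical time, from insertion to removal of the throat pack, is recorded in the same operation. Patient Assessment names application time as the primary outcome.

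Under Sample size, "This study will allow for a drop out rate 30% for the outcome variables".

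The SAP, a single paragraph in the past tense, says that every analysis used the arm to which the patient was originally assigned, and labels this intent-to-treat. It does not list who is in the analysis set. It does not mention patients without six weeks of follow-up or without a post-operative film, and it gives no counts.

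**The concern.** An inclusion criterion has to be decidable when the patient is enrolled. These two are not: whether a patient completes six weeks, or has a post-operative film, is known only after randomisation and surgery. As worded, a patient who is lost at week three was never eligible, although that patient was randomised, was operated on and has a recorded application time.

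Application time is complete when the second arch bar is in place, and nothing that happens later changes it. Excluding patients on these criteria would discard recorded primary data for no gain, and the analysed set would no longer be the randomised set. A reader of the SAP cannot tell whether that happened, because the only statement there concerns the arm in which patients are counted and not which patients are counted.

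**Working it through.** **Order of events**

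| Step | Source | When |
|---|---|---|
| Enrolment and consent | Protocol, Registration and Randomization | First consultation |
| Randomisation | Same section | After consent |
| Application time and surgical time recorded | Protocol, Therapy | During surgery |
| Post-operative film (criterion 5, second half) | Protocol, Inclusion Criteria | After surgery |
| Six weeks of follow-up reached (criterion 4) | Protocol, Inclusion Criteria | At least six weeks after surgery |

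The last two steps follow the first three. The pre-operative half of criterion 5 does not have this problem.

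**Conflict with other statements.** The Sample size section treats loss as drop-out and allows 30%. Criterion 4, read literally, treats a patient lost before six weeks as not eligible. Both cannot govern the same patient. Removing a randomised patient for later loss is also contrary to the usual meaning of intent-to-treat, which the SAP claims.

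**What the SAP sentence fixes.** It fixes the arm. An analyst could drop patients who fail criterion 4 or 5, analyse the rest as assigned, and still satisfy the explanation that the SAP gives, though not the usual meaning of the label.

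**Planned numbers.** Therapy gives 30 + 30 in the ORIF group and 20 + 20 in the CR group. 2 × 30 + 2 × 20 = 100, which agrees with 60 + 40 = 100 under Sample size. Per arm, 30 + 20 = 50. The protocol gives no effect size, SD or power, so there is no sample-size calculation to reproduce. The check below therefore uses precision only.

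**Illustration if the criteria were applied literally.** Assumptions: equal loss in both arms; a common SD; a two-sided 95% interval; loss from 0% to 30%, the upper end being the protocol's allowance and not an observed rate.

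- Patients per arm: n = 50 × (1 − loss)
- Standard error ratio: 1/√(1 − loss)
- 95% CI half-width for the difference in means, in SD units: t(0.975, 2n − 2) × √(2/n)

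| Loss | Times discarded | n per arm | SE ratio | t × √(2/n) | Half-width (SD) |
|---|---|---|---|---|---|
| 0% | 0 | 50 | 1.000 | 1.9845 × 0.2000 | 0.397 |
| 10% | 10 | 45 | 1.054 | 1.9873 × 0.2108 | 0.419 |
| 20% | 20 | 40 | 1.118 | 1.9908 × 0.2236 | 0.445 |
| 30% | 30 | 35 | 1.195 | 1.9955 × 0.2390 | 0.477 |

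By stratum, at 0% and 30% loss:

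- ORIF, 30 to 21 per arm: 2.0017 × 0.2582 = 0.517 SD, rising to 2.0211 × 0.3086 = 0.624 SD.
- CR, 20 to 14 per arm: 2.0244 × 0.3162 = 0.640 SD, rising to 2.0555 × 0.3780 = 0.777 SD.

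**The case against.** The best defence is that the literal reading is the least likely one. Therapy repeats the six-week minimum as a follow-up schedule, which suggests that criterion 4 meant agreed or expected follow-up. A 30% drop-out allowance makes little sense if a patient lost before six weeks was never eligible. Therapy records times for every study subject. The Data Safety Monitoring Plan provides for withdrawal and asks the monitor to recognise missing visits and drop-outs; it ties adherence to eligibility to risk and benefit and gives no instruction to remove data. Above all, the SAP claims intent-to-treat, which in its usual meaning keeps every randomised patient.

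Most of this stands, and it limits the point to one of wording and definition. It does not remove the point. The text of criterion 4 does not say that willingness was meant, and that reading fits a post-operative film poorly. The SAP's explanation of intent-to-treat still leaves the membership of the set unstated.

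It is also fair to say that the SAP is written after the fact, so rewording the criteria cannot change who was enrolled. The definition of the set and a count of exclusions remain useful.

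**Conclusion.** The defect in the text is certain: two conditions listed for entry can be known only after randomisation and after the primary outcome is recorded. Applied as written, they conflict with the intent-to-treat claim and with the drop-out allowance. The SAP's label points towards retention, but the SAP does not state that all randomised patients are analysed.

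Three stronger readings are tempting, and the documents do not support them.

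- **That patients were removed from the primary analysis.** No passage says so and no counts are given.
- **That the result is biased.** Bias would need exclusions, related to application time in a way that differs between arms or at different rates by arm. The documents give no information on either.
- **That the SAP is silent on retention.** It is not, because it claims intent-to-treat.

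The effect is zero if nobody was excluded. Under the stated assumptions, with the 30% allowance as an upper illustration, 30 of 100 recorded times would be lost, the standard error would rise by about 20%, and the half-width would go from 0.40 to 0.48 SD. Missing six-week healing data are ordinary attrition with or without these criteria. Severity: minor.

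**What to change.** In the protocol, restate criterion 4 as a condition that can be judged at baseline, such as agreement and ability to return for follow-up. Move the post-operative film from the criteria to the schedule of assessments.

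In the SAP, add a definition along these lines: *Application time and surgical time are analysed by assigned arm in all randomised patients with a recorded time, whatever their later follow-up. The number without a recorded time, with reasons, is reported by arm. Missing six-week data affect only the follow-up outcomes.*

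In the report, give by arm the number of randomised patients excluded on criterion 4 or 5, even if it is zero, and restore any such patients to the analysis of application and surgical time.

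The cost is one count of exclusions and missing times by arm, two or three SAP sentences and the rewording of two criteria. No further patients, visits or data are needed.

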### Exclusion Criteria:

- 1) Comminuted fractures
- 2) Infected fractures
- 3) Previously treated fractures
- 4) Complete edentulism
- 5) Gun shot wounds
- 6) Pregnancy or breast feeding

Informed consent will be obtained on all patients. Any patient who declines to participate in this study will be treated in an identical fashion to those who enroll in this study other than the type of intra-operative MMF will be determined by the attending surgeon rather than randomized.

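### Tooth number is neither a listed variable nor a pre-specified covariate, and the primary comparison of application time makes no use of the ORIF/CR strata, so precision is given away

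*Protocol*

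**What the plan says.** **Devices.** The protocol's Introduction separates the two bars partly by their dependence on teeth. Of the control it says that "the application of Erich arch bars is time-consuming and requires the presence of teeth". Of the hybrid bar, which is screwed to bone, it says: "This potentially reduces the time required to place the arch bars as well as the need for teeth". The Schema adds that "Erich arch bars will be placed using a combination of 24 and 25 gauge wire as is the historical technique".

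**Eligibility and allocation.** The only dentition criterion is the exclusion "Complete edentulism". Patients with some teeth missing are therefore eligible for both arms. On stratification the Schema says: "All eligible subjects will be initially stratified to ORIF or CR". Dentition is not a stratum.

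**Outcome and data.** "The primary outcome variable is time required to place the arch bars". The protocol's Patient Assessment section gives the baseline list: "Preoperative variables include medical history (DM and HIV), social history, fracture location, number of fractures, time from injury to surgery and antibiotic use". Tooth number is not in that list, and the operative variables named there do not include the device actually placed. The Data Collection section refers to an attached data sheet, which is not in the text available for this review.

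**Analysis.** The SAP compares application time between treatment groups by t-test. It then describes a multiple regression whose covariates are picked by stepwise selection and not named. Patients are analysed as assigned. The SAP does not mention the ORIF/CR strata, and neither document says how a crossover would be recorded or reported.

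**The concern.** The protocol's own rationale says that one device needs teeth to hold it and the other may need them less. The control is wired and the outcome is the time taken to place it, so the number of teeth could plausibly affect that outcome, in either direction. A baseline variable of this kind is normally recorded and named in advance as a covariate. Here it is not on the list, and a variable that is not collected cannot enter a stepwise selection.

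The same analysis leaves out the one factor that the design does control. Randomisation is stratified by ORIF/CR, but the t-test as written does not use the strata, and stepwise selection may or may not bring them in.

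At stake are the width of the confidence interval for the primary time difference, the effect of a chance imbalance in dentition, and whether a reader can tell how many patients received the bar they were assigned.

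**Working it through.** **1. The plan's own figure.** The Therapy section gives 30 + 30 = 60 ORIF and 20 + 20 = 40 CR patients, 100 in all, or 50 per bar type. This agrees with the Sample size section. No effect size, standard deviation (SD) or power is stated there, so 100 can be added up but not derived. Application time is measured during surgery, so I use 50 per arm without the 30% dropout allowance.

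**2. Precision gained by adjusting for tooth number.** If tooth number explains a share R² of the within-arm variance, adjustment multiplies the standard error by √(1 − R²), which is worth 1/(1 − R²) times the sample. The documents give no R²; the values are assumptions. The power column uses a normal approximation, two-sided α = 0.05 (the SAP gives 0.05 but not the sidedness), and a true difference of 0.56 SD. That difference is (1.96 + 0.84) × √(2/50), the one detectable with 80% power at 50 per arm without adjustment.

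| Assumed R² | SE factor | SE reduction | Equivalent N (100 actual) | Power |
|---|---|---|---|---|
| 0 | 1.000 | 0% | 100 | 80% |
| 0.10 | 0.949 | 5% | 111 | 84% |
| 0.20 | 0.894 | 11% | 125 | 88% |
| 0.30 | 0.837 | 16% | 143 | 92% |

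**3. Chance imbalance in tooth number.** The difference in mean tooth number between arms has a 95% range of ±1.96 × √(2/n) SD:

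- 50 per arm: ±0.39 SD
- ORIF, 30 per arm: ±0.51 SD
- CR, 20 per arm: ±0.62 SD

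The resulting shift in the unadjusted time difference is the imbalance times the correlation √R². At the edge of the overall range this is 0.392 × √0.10 = 0.12 SD of application time for R² = 0.10, and 0.392 × √0.30 = 0.21 SD for R² = 0.30. The shift averages zero over randomisations; adjustment removes it from the one trial that is run.

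**4. The strata.** Allocation is equal within ORIF and within CR, so a difference between the two procedures in mean application time does not bias the comparison. It does inflate the SD used by a pooled t-test. With a 60:40 split and a procedure difference of Δ within-stratum SDs, the pooled variance is 1 + 0.6 × 0.4 × Δ² = 1 + 0.24Δ². The documents give no Δ. If it is zero, nothing is lost; otherwise the t-test's standard error is too large.

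**5. Cost in degrees of freedom.** The t-test leaves 100 − 2 = 98 residual degrees of freedom. A model with treatment, ORIF/CR and one tooth-count term leaves 100 − 4 = 96.

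**The case against.** **No inconsistency.** Requiring teeth and excluding patients who have none agree with each other. This stands. The point concerns data and analysis, not a contradiction in eligibility.

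**Not proven unrecorded.** The data sheet may hold a tooth count, and the Patient Assessment lists may be summaries. This stands too. The supportable statement is that tooth number is not among the listed variables and not pre-specified as a covariate.

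**The Introduction does not say that tooth number drives application time.** It names less time and less need for teeth as two separate benefits, and fewer teeth could mean fewer wires and a faster Erich placement. This is correct, which is why R² is shown as an assumption and an interaction term belongs in a secondary analysis. Adjustment does not need the direction to be known.

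**A stronger reading a reader might infer.** Sparsely dentate patients assigned to Erich bars might receive the hybrid bar instead, and analysis as assigned would then shrink the time difference. The documents do not support this:

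- They give no crossover rate. They also say nothing about when the hybrid bar's screw minimum cannot be met, so one-way crossover is not established.
- An abandoned Erich attempt followed by hybrid placement could take longer and widen the difference.
- The power loss depends on the effect assumed. If 10% or 20% of the Erich arm crossed over and took the average hybrid time, power would fall from 80% to 71% or 61% at 0.56 SD, but would remain 95% or 89% at 0.8 SD.

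Nor does it follow that a surgeon should confirm before randomisation that either bar could be placed. That would be an unwritten clinical threshold which narrows the population, possibly by removing patients in whom the Introduction expects the hybrid bar to help.

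**Validity is not threatened.** Randomisation balances dentition in expectation. This stands and limits the point to efficiency and interpretation.

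**Conclusion.** The point holds as a matter of precision and interpretation, not bias. The primary comparison uses neither the stratification factor nor a baseline variable that the protocol's rationale marks as relevant, and it leaves covariate choice to a stepwise procedure.

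If tooth number explains 10% to 30% of the variance in application time, adjustment cuts the standard error by 5% to 16%, equivalent to 11% to 43% more patients. The R² range is assumed; if tooth number explains little, the gain is small. The gain from ORIF/CR cannot be sized from the documents, but that factor is already known for every patient.

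Two limits apply. Absence from the data sheet could not be checked, and no claim is made about how often crossover occurs or which way it would move the result.

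**What to change.** 1. **Primary model.** Replace the t-test and the stepwise selection for application time with one pre-specified linear model: time on treatment, ORIF/CR and tooth count (total over both arches, one linear term). Report the adjusted difference with its 95% confidence interval.
2. **Tooth count.** Count teeth per arch on the preoperative panoramic film required by inclusion criterion 5 and add the count to the data sheet if it is not there. The Pretreatment Evaluation section allows a panoramic film or a CT scan, so confirm that the film exists for every patient.
3. **Device placed.** Record the bar actually placed and report crossovers by arm and in each direction. Keep the analysis by assignment.
4. **Secondary analysis.** Add a treatment-by-tooth-count term, because teeth may matter mainly for wired bars and a common slope would then be too simple.
5. **Dentition criterion.** Have the investigators state how the existing exclusion fits with the Introduction's remarks on teeth. No threshold is proposed here.
6. **Timing.** The SAP is dated November 2018 and written in the past tense. If enrolment is complete, count from the stored films and label the tooth-count adjustment post hoc. Adjustment for ORIF/CR can still be justified from the randomisation scheme.

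**Cost.** One data item from an existing film, a field for the device placed, and one degree of freedom each for tooth count and ORIF/CR. The downside is little return if tooth number explains little of the variance.
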